5.3. Procedures for Maintaining and Breaking the Masking

The test articles mask shall not be broken unless information concerning the lens type is necessary for the urgent medical treatment of a subject. The Sponsor must be notified before the mask is broken. The Biostatistician performing the interim analysis should keep the decode information in a secure location and should not share it with the personnel involved in the study until the all subjects have completed the study and the database is finalized.

When dispensing test articles, the following steps should be followed to maintain randomization codes:

1. Investigator or designee (documented on the Delegation Log) will consult the lens fitting schedule/randomization scheme to obtain the test article assignment for that subject prior to dispensing
2. Investigator or designee will record the subject's number on the appropriate line of the randomization scheme
3. Investigator or designee will pull the appropriate test articles from the study supply. All test articles that are opened, whether dispensed (placed/fit on eye or dispensed outside the clinical site) or not, must be recorded on the Test Article Accountability Log in the "Dispensed" section.

Clinical Study Protocol

Johnson & Johnson Vision Care, Inc.

6. STUDY INTERVENTION

6.1. Identity of Test Articles

The following contact lenses will be used in this study:

Table 2: Test Articles

	Test	Control
Name	senofilcon A with novel manufacturing technology	senofilcon A with current manufacturing technology
Manufacturer	JJVC - 4GT	JJVC - 4GT
Lens Material	senofilcon A	senofilcon A
Nominal Base Curve @ 22°C	8.5	8.5
Nominal Diameter @ 22°C	14.3	14.3
Nominal Distance Powers (D)	-0.50 to -3.25 And -3.75 to -6.00 in 0.25 steps	-0.50 to -3.25 And -3.75 to -6.00 in 0.25 steps
Wear Schedule in Current Study	Daily wear	Daily wear
Replacement Frequency	Daily disposable	Daily disposable
Packaging Form (vial, blister, etc.)	Sterile blister pack	Sterile blister pack

Each subject will wear approximately 14 of each lens type.

6.2. Ancillary Supplies/Products

The Sponsor will provide sterile rewetting drops for subject use if needed to relieve dryness. Subjects should not use their habitual rewetting drops during the study.

The following solutions may be used in this study:

Table 2: Ancillary Supplies

	Solution
Solution Name/Description	Single use EyeCept or LacriPure or ScleralFil
Manufacturer	OPTICS Laboratory Inc/Menicon/ B+L
Preservative	None

6.3. Administration of Test Articles

[figure not shown]
Test articles will be dispensed to subjects meeting all eligibility requirements, including any dispensing requirements set forth in this clinical protocol. Subjects will be dispensed an adequate supply of test articles to complete the study. Lost or damaged test articles may be replaced at the discretion of the Investigator and/or the Sponsor.

Clinical Study Protocol

Johnson & Johnson Vision Care, Inc.

6.4. Packaging and Labeling

The test articles will be packaged in blisters as the primary packaging. The test article will be over-labeled to mask the subject/Investigators to the identity of the lens. The test articles will be in investigational cartons sealed with a tamper evident seal, commercial cartons, or in plastic bags as the secondary packaging form. The sample study label is shown below:

6.5. Storage Conditions

Test articles will be maintained at ambient temperatures at the clinical site. Test articles must be kept under secure conditions.

6.6. Collection and Storage of Samples

Lenses that are being collected will be stored wet (using saline solution) in separate glass vials with labels that minimally contain study number, date, subject number, and eye from which the lens was removed.

When possible, any lens or test article associated with an Adverse Events and/or a Product Quality Complaint must be retained and stored in a glass vial with moderate solution pending directions from the sponsor for potential return back to JJVC

6.7. Accountability of Test Articles

JJVC will provide the Investigator with sufficient quantities of study articles and supplies to complete the investigation. The Investigator is asked to retain all lens shipment documentation for the test article accountability records.

Test articles must be kept in a locked storage cabinet, accessible only to those assigned by the Investigator for dispensing. The Investigator may delegate this activity to authorized study site personnel listed on the Site Delegation Log. All test articles must be accounted. This includes:

Clinical Study Protocol

Johnson & Johnson Vision Care, Inc.

1. What was dispensed for the subject for trial fitting, to wear out of the office, or issued for the subject to replace appropriately between visits.
2. What was returned to the Investigator unused, including expired or malfunctioning product.
3. The number and reason for unplanned replacements.

The Investigator will collect all unused test articles from the subjects at the end of the subject's participation. Subject returned unused test articles must be separated from the clinical study inventory of un-dispensed test articles and must be labeled with the subject number and date of return. Following final reconciliation of test articles by the monitor, the Investigator or monitor will return all unused test articles to JJVC.

If there is a discrepancy between the shipment documents and the contents, contact the study monitor immediately.

7. STUDY EVALUATIONS

7.1. Time and Event Schedule

Table 3: Time and Events

	Visit 1 (Day 0)		Visit 2 (Day 5-9 from Visit 1)	Visit 3 (After a 7-9 day wash-out period)		Visit 4 (Day 5-9 from Visit 3)
Estimated Visit Duration	1.5 Hours		1 Hour	1 Hour		1 Hour
Event	Baseline	Trial #1 Dispense	Trial #1 Follow-up Visit	Post Washout Baseline	Trial #2 Dispense	Trial #2 Follow-up Visit and Exit
Study Informed Consent	X					
Demographics	X					
Medical History	X			X		
Eligibility Assessment	X			X		
Background CLUE Questionnaire	X					
Subject Reported Symptoms	X	X	X	X	X	X

Clinical Study Protocol
Johnson & Johnson Vision Care, Inc.

	Visit 1 (Day 0)		Visit 2 (Day 5-9 from Visit 1)	Visit 3 (After a 7-9 day wash-out period)		Visit 4 (Day 5-9 from Visit 3)
Estimated Visit Duration	1.5 Hours		1 Hour	1 Hour		1 Hour
Event	Baseline	Trial #1 Dispense	Trial #1 Follow-up Visit	Post Washout Baseline	Trial #2 Dispense	Trial #2 Follow-up Visit and Exit
Distance Visual Acuity	X	X	X	X	X	X
Spherocylindrical Refraction & VA	X					
Biomicroscopy & Eye Rinse	X		X	X		X
Study Lenses Dispensed		X			X	
Lens Damage		X	X		X	X
10 minutes settling		X			X	
Spherical Over- Refraction		X			X	
logMAR visual acuity (ETDRS charts)		X	X		X	X
Lens Fit Assessment		X	X		X	X
Lens Surface Deposits & Lens Wettability Assessment		X	X		X	X
Compliance			X			X
Contact Lens Wear Time	X		X	X		X
Follow-up CLUE Questionnaire			X			X
Adverse Event Review			X			X
Concomitant Medication Review	X		X	X		X
Study Completion						X

Clinical Study Protocol

Johnson & Johnson Vision Care, Inc.

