4. STUDY DESIGN AND RATIONALE

4.1. Description of Study Design

This study is a multi-site, randomized, double-masked, 2×2 crossover design, 1-week dispensing study. Subjects will wear bilaterally both Test and Control lenses in a random order for 1-week each as a daily disposable modality with a wash-out period of 1 week between the wearing periods.

Period 1:

At study Visit 1, subjects will be consented and screened for inclusion/exclusion criteria. If a subject is found to meet all eligibility criteria (see Section 3.4.), they will be randomly assigned to either Test/Control or Control/Test sequence using 1:1 ratio (i.e. 1/2 of subjects on the Test/Control sequence and 1/2 on the Control/Test sequence). Subjects will fit the first pair of lenses in both eyes based on the sequence assigned; otherwise, the subject will be deemed ineligible for this study. Subjects will be advised to wear the study lenses at least 8 hours a day for a minimum of 5 days.

Successfully dispensed subjects at the Visit 1 will be scheduled for a follow-up visit (Visit 2). The follow-up visit will occur approximately 7 ± 2 days after the Visit 1. Unscheduled follow-up visits may occur during the study. At this visit, CLUE comfort and vision, slit lamp findings will be captured.

Wash-out period:

After completion of Visit 2, there is a 7 to 9 days washout period during which subjects may use their habitual products.

Period 2:

Following the washout period, the subject returns for Visit 3 and post-washout baseline evaluation will take place prior to lens fitting. After baseline evaluation, subject will be fitted and dispensed with the second pair of lenses in the assigned sequence. Subjects will be advised to wear the study lenses at least 8 hours a day for a minimum of 5 days.

Visit 4 takes place 7 ± 2 days after Visit 3, at which CLUE comfort and vision, slit lamp findings, final evaluation will take place.

Both study lenses will be worn as a daily disposable modality. JJVC will provide the investigational sites with sufficient quantities of study lenses and supplies to complete the study.

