2.12	Lens Removal	
The lenses will be removed and stored in the following manner:
 
The OD and OS lenses will be stored wet (using saline solution) in separate glass vials with labels that minimally contain study number, date, subject number, and eye from which the lens was removed in a study specific refrigerator.
 
(Temperature monitoring of refrigerator not required)
 
*The lenses will be shipped back to the Sponsor ambiently once the study has completed.
	
2.13	Slit Lamp Biomicroscopy	
FDA Slit Lamp Classification Scale will be used to grade the findings and determine eligibility.
 
Limbal and Bulbar Conjunctival Hyperemia findings and detailed Corneal Staining Assessment will be recorded using a more detailed scale for internal purposes only.
 
Conjunctival hyperemia should be assessed using the 0.5 increment grading scale.
	
2.14	Eye Rinse	The investigator or technician may rinse the subject's eyes with sterile saline.	
2.15	Visual Acuity	Record the distance Snellen visual acuity with their habitual contact lenses or spectacles (OD, OS, and OU) to the nearest letter. Subjects must read the smallest line until at least 50% of the letters are read incorrectly.	
2.16	Instructions	The subject will be instructed to wear their habitual lenses for 7-9 days.	

Clinical Study Protocol
Johnson & Johnson Vision Care, Inc.

VISIT 3

Subjects should attend wearing their habitual lenses.

Visit 3: Post Wash-out Baseline			
Step	Procedure	Details	
3.1	Medical History and Concomitant Medications	Questions regarding the subjects' medical history and concomitant medications.	
3.2	Background CLUE Questionnaire	Subject will complete questions regarding their experiences with their habitual lenses.	
3.3	Contact lens wear times	Record the current wear time (WT) and comfortable wear time (CWT).	
3.4	Subject-reported Ocular Symptoms	Subject Reported Ocular Symptoms and Problems	
3.5	Distance visual acuity (VA)	Record the distance Snellen VA for OD, OS and OU. Subject must keep reading smaller lines until less than half the letters are correctly identified.	
3.6	Remove habitual lenses	The subject's habitual lenses will be removed and stored in their own lens case. If they forgot to bring their lens case, one will be provided to them.	

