3.7	Biomicroscopy	
FDA Slit Lamp Classification Scale will be used to grade the findings and determine eligibility. If any of these slit lamp findings are Grade 3 or higher, the subject is discontinued from the visit as ineligible and may be rescheduled for another baseline visit for the randomization period.
 
Limbal and Bulbar Conjunctival Hyperemia findings and detailed Corneal Staining Assessment will be recorded using a more detailed scale for internal purposes only.
 
Conjunctival hyperemia should be assessed using the 0.5 increment grading scale.
	
3.8	Eye Rinse	The investigator or technician may rinse the subject's eyes thoroughly with sterile saline.	
3.9	Continuance	
All responses to Exclusion Criteria questions must be answered "no" for the subject to continue.
 
One additional baseline examination is permitted to be performed if the subject does not meet the eligibility criteria at the initial baseline visit
	

Clinical Study Protocol
Johnson & Johnson Vision Care, Inc.

Visit 3: Post Wash-out Baseline		
Step	Procedure	Details
		If subject is deemed to be ineligible after baseline, proceed to Final Evaluation and complete all forms.

Visit 3: Treatment 2 Fitting		
Step	Procedure	Details
3.10	Lens Selection	
Assign the study lens based on the randomization scheme.
 
Select the contact lens power based on vertex-corrected subjective best sphere refraction.

3.11	Lens Insertion	
The Investigator or the subject inserts the study lenses. Record the time of lens insertion.
 
Check for lens damage under the slit lamp before proceeding with lens settling.
 
Note: A PIG will be given to the subject in any study where a lens is placed on eye.

3.12	Lens damage	
Using the slit lamp, assess lenses for damage. If any defects are noted, investigator should complete a Product Quality Complaint in EDC.
 
Damaged lenses will be removed and stored in the following manner: The OD and OS lenses will be stored wet (using saline solution) in separate glass vials with labels that minimally contain study number, date, subject number, and eye from which the lens was removed.
 
Replace lens if damaged.

3.13	Lens Settling	Allow the study lenses to settle for a minimum of 10 minutes.

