3.19	White Light Lens Surface Wettability	Record the white light lens wettability of both lenses.
3.20	Surface Deposits	Record any front and back surface lens deposits.
Visit 3: Treatment 2 Lens Dispensing		

Clinical Study Protocol
Johnson & Johnson Vision Care, Inc.

Visit 3: Treatment 2 Fitting		
Step	Procedure	Details
Step	Procedure	Details
3.21	Exit VA	Record subjects' distance Snellen visual acuity, OD, OS, and OU to the nearest letter.

Visit 3: Lens Dispensing		
Step	Procedure	Details
3.22	Continuance	
For the subject to continue in the study, they must meet all three of the following criteria:
 
 • Visual acuity is 20/30 or better OD and OS • The lens fit is acceptable OD and OS • Investigator approval 
If the Investigator does not approve the dispensing of the first study lens, then the study is terminated for that subject.

3.23	Dispense	
The lenses will be dispensed for a 5-9 day wearing period. During this time, they are required to wear the lenses at least 5 days and at least 8 hours per day that they are worn.
 
 • Dispense enough lenses to last the subject to their scheduled follow-up visit. Do not dispense extras* • The lenses will be worn as daily wear/daily disposable only • Rewetting drops are permitted if needed • Subjects will be scheduled for their 1-week follow-up visit and bring their habitual correction with them • Subjects should be instructed to wear the study lenses to the follow-up visit 
* Note: In the event a lens is lost or damaged, the subject will return to the clinical site for replacement. As much as reasonably possible, a damaged lens and packaging should be returned to the clinical site (wet, if possible) and then returned to the Sponsor. If lens damage is present, complete the Product Quality Complaint Form. The lens will be stored in labeled vial with saline, and clearly differentiated from the other worn lenses that will be shipped back to the Sponsor.

Clinical Study Protocol
Johnson & Johnson Vision Care, Inc.

VISIT 4

Subjects should attend wearing their study lenses.

Visit 4: Treatment 2 Follow-Up Visit		
Step	Procedure	Details
4.1.	Adverse Events and Concomitant Medications Review	Review any changes to the subject's medical history or concomitant medications from the previous study visit. Record any changes, and any adverse events.
4.2.	Wearing Time	Record the average wearing time and comfortable wearing time.

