13.3. Documentation and Follow-Up of Adverse Events

The recording and documenting of adverse events (ocular and non-ocular) begin when the subjects are exposed to the test article, study treatment or study procedure. Adverse events reported before the use of test article, start of study treatment, or study procedures will be recorded as medical history. However, if the condition deteriorates at any time during the study it will be recorded and reported as an AE. Untoward medical events reported after the subject's exit from the study will be recorded as adverse events at the discretion of the Investigator.

Upon finding an adverse event, the Principal Investigator will document the condition in the subject record and in the eCRFs. He/she will complete the Adverse Event /eCRF.

Complete descriptions of all adverse events must be available in the subject record. All Adverse Events including local and systemic reactions not meeting the criteria for "serious adverse events" shall be captured on the appropriate case report form or electronic data system.

Clinical Study Protocol **Johnson & Johnson Vision Care, Inc.**

All adverse events occurring while the subject is enrolled in the study must be documented appropriately regardless of relationship.

It is the Investigator's responsibility to maintain documentation of each reported adverse event. All adverse events will be followed in accordance with applicable licensing requirements. Such documentation will include the following:

- Adverse event (diagnosis not symptom).
- Drawings or photographs (where appropriate) that detail the finding (e.g., size, location, and depth, etc.).
- Date the clinical site was notified.
- Date and time of onset.
- Date and time of resolution.
- Adverse event classification, severity, and relationship to test articles, as applicable.
- Treatment regimen instituted, including concomitant medications prescribed, in accordance with applicable licensing requirements.
- Any referral to another health care provider if needed.
- Outcome, ocular damage (if any).
- Likely etiology.
- Best corrected visual acuity at the discovery of the event and upon conclusion of the event.

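### No explicit adverse event review is scheduled at Visit 3, so no dedicated review covers the 7-9 day washout, although section 13.3 requires every event during enrollment to be documented

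*Combined protocol and SAP*

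**What the plan says.** Table 3 in section 7.1 lists "Adverse Event Review" as a scheduled event, with marks at Visit 2 and Visit 4. Both Visit 3 columns (post-washout baseline and second dispensing) are blank in that row. Concomitant medication review is marked at the Visit 3 baseline.

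The visit steps in section 7.2 agree with the table. Steps 2.1 and 4.1 are joint reviews of adverse events and medications. Each begins "Review any changes to the subject's medical history or concomitant medications from the previous study visit" and then asks the site to record changes and adverse events. Step 3.1 reads only "Questions regarding the subjects' medical history and concomitant medications", which is the wording of screening step 1.3, before any study lens has been worn.

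On the interval itself, section 4.1 says: "After completion of Visit 2, there is a 7 to 9 days washout period during which subjects may use their habitual products". It also says: "Visit 4 takes place 7 ± 2 days after Visit 3".

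Section 13.3 sets the general duty: "All adverse events occurring while the subject is enrolled in the study must be documented appropriately regardless of relationship".

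**The concern.** Subjects are still enrolled during the washout, and have just finished a week on the first study lens. Section 13.3 therefore counts adverse events in that interval, but the schedule gives the site no step that asks for them when the interval ends. Visit 3 is the only scheduled visit after the day of first exposure with no adverse event review.

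Three things are at stake:

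- **Ascertainment.** Adverse events are a listed endpoint (synopsis and section 2.2) and bear on study termination (section 11). Events that are not prompted for tend to be under-recorded.
- **Timing.** Section 13.4 sets reporting limits of 24 hours or 2 days, but they run from discovery. An event first elicited at Visit 4 instead of Visit 3 is discovered 5-9 days later, after the second lens has been dispensed.
- **Period.** A washout event first raised at Visit 4 may be summarized with the second lens. One raised at Visit 3 under a history heading may be entered as history.

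**Working it through.** The plan states no figure for this point. The check is a comparison of the schedule with the steps, followed by day arithmetic.

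**1. Table against steps.** The two do not always match: the background CLUE questionnaire is step 3.2 but is not marked at Visit 3 in Table 3. A blank cell alone would not settle the question. Here both sources agree.

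| Visit | Review marked in Table 3 | Step | Adverse events named in the step |
|---|---|---|---|
| 2 | yes | 2.1 | yes |
| 3 | no | 3.1 | no |
| 4 | yes | 4.1 | yes |
| Unscheduled | not in table | U.2 | yes (optional) |
| Final Evaluation | not in table | F.1-F.2 | no |

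Section 15.1 says the electronic forms are designed around each visit's procedures. A Visit 3 form built from these steps would carry no adverse event prompt.

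**2. What Visit 3 does capture before fitting.**
- Step 3.1: history and medications.
- Step 3.4: "Subject Reported Ocular Symptoms and Problems", which is ocular only.
- Step 3.5: visual acuity.
- Step 3.7: graded slit lamp examination, which sees signs still present on the day.
- Step 3.9: exclusion criteria.

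For ocular problems still present, this is substantial. For events that have resolved, or are not ocular, only the history and medication questions could bring them out.

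Step 3.7 also shows the missing link to event recording. It says "If any of these slit lamp findings are Grade 3 or higher, the subject is discontinued from the visit as ineligible" and allows rescheduling, with no mention of an adverse event form. Section 13.1 lists grade 3 or higher corneal findings among significant adverse events.

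**3. Days without a dedicated review.** Inputs from section 4.1 and Table 3: Visit 2 at day 5-9 from Visit 1, washout 7-9 days, Visit 4 at day 5-9 from Visit 3.

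- Visit 3 falls on day 5+7 = 12 to 9+9 = 18.
- Visit 4 falls on day 12+5 = 17 to 18+9 = 27.
- Washout share = washout days / (period 1 + washout + period 2).
- Nominal: 7 / (7+7+7) = 7/21 = 33%.
- Smallest: 7 / (9+7+9) = 7/25 = 28%.
- Largest: 9 / (5+9+5) = 9/19 = 47%.

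These shares use the planned windows. Section 10 treats a washout of 10-15 days as a minor deviation, so some retained subjects could have a longer interval.

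**The case against.** A reader might infer something stronger: that Visit 4 looks back only to Visit 3, so washout events fall in no review window and are never asked about. The documents do not support that, for four reasons.

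- In step 4.1 the limit to the previous visit is attached to changes in history and medications. The following instruction to record adverse events carries no date limit, so a site could properly record a washout event there.
- Visit 3 is not empty of safety checks. A history and medication interview can bring out a resolved event, and the symptom, acuity, slit lamp and exclusion checks all precede fitting. Dispensing also needs investigator approval (step 3.22).
- Section 13.3 reserves medical history for events reported before the test article, treatment or procedures began. Entering a washout event as history would be a site error against the text, not something the plan directs.
- Sponsor reporting under section 13.4 applies whenever an event is discovered, and unscheduled visits may include an adverse event review.

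Nor do the documents say that washout events belong to the first lens. Subjects are on habitual lenses then, relatedness is judged case by case (section 13.2.1), and onset date and time are recorded (section 13.3). A recorded event can therefore be placed in the washout.

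It can also be said that adverse events are evaluated only descriptively in a feasibility study, so no hypothesis test turns on this row. That is correct, and it limits the weight of the point.

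All of this shows that the duty to record exists and that some routes to it are open. It does not supply a prompt at the visit that closes the washout, when the same prompt is written into the other two follow-up contacts.

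**Conclusion.** The point holds as a missing explicit prompt, not as a missing duty to record. As written, no dedicated adverse event review covers the washout: about 7 of 21 nominal days, or 28% to 47% across the planned windows. The likely effects are some under-ascertainment, chiefly of resolved or non-ocular events; reporting up to 5-9 days later than need be; and occasional attribution to the wrong period.

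The number of events affected cannot be estimated, because the documents give no event rate and the other Visit 3 checks will catch some. The percentages describe calendar time only. They rest on reading the step 4.1 look-back as applying to adverse events as well as to history; on the looser reading, the washout is covered at Visit 4, but late and by inference.

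The co-primary and secondary analyses are unaffected. This is a cheap improvement that should be made, because events not asked about at the time are hard to recover afterwards.

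**What to change.** - In Table 3, add an X for adverse event review under Visit 3, Post Washout Baseline.
- In step 3.1, use the step 2.1 wording: review changes since the previous visit and record any adverse events. Carry the same prompt into the Visit 3 electronic form.

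A useful companion, not needed for the point to hold, is one sentence in section 14 stating to which lens or period an event with onset in the washout is assigned in the summaries.

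The cost is one table cell, one reworded step, one more form prompt and about a minute per subject at a visit already scheduled. There is no effect on sample size, visit timing or the planned analyses.
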